## 2 Objectives and Endpoints

We propose to determine the effects of LDE225 on neoplastic prostate tissue from men at high risk of systemic disease progression, by comparing pre-surgical core-biopsy specimens to tumor tissue harvested at the time of prostatectomy. In addition to assaying drug-related on-target effects (i.e. *GLI* expression changes) we propose to determine the effects of Smo inhibition on the prostate cancer transcriptome.

### Primary Objective

- (1) To determine the pharmacodynamic (PD) effects of LDE225 on resected prostate tissue from men undergoing radical prostatectomy for high-risk localized prostate cancer (as measured by reductions in *Gli1* mRNA expression).

### Secondary Objectives

- (1) To determine whether presurgical treatment with LDE225 can exert a pathological effect on high-risk tumors (i.e. increase apoptosis, decrease proliferation).
- (2) To evaluate whether presurgical treatment with LDE225 diminishes the risk of PSA recurrence following prostatectomy.
- (3) To evaluate the safety and tolerability of LDE225 in the presurgical setting.

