### Exploratory Objectives

- (1) To evaluate genome-wide mRNA expression changes in prostate cancer induced by LDE225 exposure.

The objectives and related endpoints are summarized in the [Table](#) below.

	Objective	Endpoint	Analysis
Primary	Pharmacodynamic effect of LDE225 on prostate tissue	50% reduction in Gli1 mRNA expression comparing pre-operative prostate biopsies to radical prostatectomy specimens	qRT-PCR performed on pre-operative tumor biopsy specimens and tumor from RP specimens. Comparison performed within and between treated and untreated groups. Correlation of Gli1 levels to pre-operative Gli1 expression.
Secondary	
 
-Pathological effect on localized high-risk cancer
 
-To determine whether pre-surgical treatment with LDE225 diminishes the risk of PSA recurrence following prostatectomy
 
-To evaluate drug-related toxicities including peri-operative complications
 
	
 
-Assessment of tumor stage and grade (predicted versus actual) and changes in proliferation and apoptosis
 
-PSA <math>\geq 0.2</math> ng/ml at 3 months following prostatectomy
 
-Length of surgery, intraoperative blood loss, length of hospital stay, rates of post-operative complications (infection, wound breakdown, deep vein thrombosis, within 90 days from surgery)
 
	
 
-Routine pathologic analysis. Additionally, semi-quantitative IHC for Ki-67 and cleaved caspase-3. Comparison performed within and between treated and untreated groups.
 
-Routine serum ELISA for PSA
 
-Comparison of routinely collected intraoperative and post-operative data between treated and untreated groups
 

Exploratory	Evaluate genome-wide mRNA expression changes in prostate cancer induced by LDE225 exposure	Gene expression analysis on biopsy and prostatectomy tissue using the Affymetrix GeneChip Human Exon 1.0ST Array	Differential gene expression analysis and analysis of functional annotation comparing biopsy and prostatectomy specimens both between and within groups

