## 6 Schedule and Assessments

### 6.1 Study flow and visit schedule

	Screening Evaluation	Repeat Biopsy a	Day 1	Day 14	Prostatectomy, Day 28 ( $\pm 3$ )	Follow-up, 1 mo Post-Op	Follow-up, 2 mo Post-Op	Follow-up, 3 mo Post-Op j
Informed consent	X							
Medical history	X			X	X			
Medication review	X			X	X			
Physical exam	X			X	X			X
Vital signs	X			X	X			X
Height and weight	X			X	X			
Performance status	X			X	X			X
ECG	X			X	X			
CT and bone scan b	X							
Heme labs, Coags c	X			X	X			X
Chemistries, incl. CK d	X			X	X			X
PSA (standard) e	X				X			X
PSA (ultrasensitive) e						X	X	
Plasma for PKs f	X				X			
LDE225 dose g (Arm 1)				X-----X				
Observation g (Arm 2)				X-----X				
Toxicity assessment				X-----X				
Prostatectomy specimen h					X			
Pathologic review i	X	X			X			

a: A repeat 12-core (pre-treatment) prostate biopsy should be conducted within 4 weeks ( $\pm 4$  days) of starting protocol therapy. Tissue will be subject to mRNA analysis.  
b: Staging CT (if allergic to CT scan contrast, obtain MRI with contrast); CT and Bone scan must be performed within 2 months of starting protocol therapy  
c: Hematology laboratories include hemoglobin, hematocrit, white blood cell count with differential, and platelets. In addition, PT/INR and APTT should be collected.  
d: Chemistry laboratories include sodium, potassium, chloride, bicarbonate, urea nitrogen, creatinine, glucose, calcium, albumin, total protein, bilirubin, alanine aminotransferase (ALT), aspartate aminotransferase (AST), and alkaline phosphatase. In addition, creatine kinase (CK) should be measured at baseline, and then only for patients receiving LDE225.. Samples drawn for CK levels will be taken from both arms.  
e: Serum PSA should be obtained pre-treatment and on the day of surgery, and at 1, 2 and 3 months post operatively. Ultrasensitive PSA testing should be run at the 1 and 2 month post-op time points.  
f: Blood samples will be collected at baseline and on the day of prostatectomy for measurement of plasma LDE225 levels.  
g: LDE225 800 mg by mouth once daily (for 4 weeks,  $\pm 3$  days) OR observation. Patients randomized to the observation arm are not required to have the C1D14 visit.  

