h: Radical prostatectomy specimens to be processed at Johns Hopkins according to standard procedures, with additional 250-mg biopsies of prostate tissue frozen for analysis of mRNA expression and tissue LDE225 levels.  
i: Pathological review of outside biopsy slides at the Johns Hopkins Hospital are required to confirm Gleason grade of disease at screening. Pathologic evaluation will also occur with frozen tissue from repeat biopsies and with tissue from radical prostatectomy.  
j: The post-operative evaluation at 1 and 2 months after prostatectomy may take place over the telephone or in person, but patients are required to have labs collected as indicated above. The 3-month follow-up should involve an office visit. After the 3-month visit, PSA will continue to be collected according to the treating physician's standard practice (usually once every 3 months).

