## **6.2 Assessments**

### **6.2.1 Efficacy assessments**

The primary measures of efficacy in this trial are pharmacodynamic measured by the change in *Gli1* expression by qRT-PCR. In addition, efficacy will also be evaluated in secondary endpoints which will compare tumor stage, grade, surgical margin rates and tumor proliferation / apoptosis between treatment and observation arms. The proportion of patients with undetectable PSAs at three months will also be assessed in the two groups.

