### **8.2      Analysis of the secondary endpoints**

- **Apoptotic markers.** Caspase 3 staining (and/or TUNEL assay results) will be expressed as the mean staining percentage in tumor samples, and reported separately for each treatment group. Standard deviations, 95% confidence intervals, and ranges will also be reported where appropriate. Means will be compared across treatment arms using two-way ANOVA.
- **Proliferation markers.** Ki-67 staining will be expressed as the mean staining percentage in tumor samples, reported separately for each treatment arm. Standard deviations, 95% confidence intervals, and ranges will also be reported where appropriate. Means will be compared across treatment arms using two-way ANOVA.
- **Pathological complete responses (pCR).** This will be defined as an absence of tumor identification on standard histological analysis of the resected prostate specimens. The proportion of patients achieving a pCR will be compared between treatment arms using the Mantel-Haenszel test.

- **PSA response rates.** This will be defined as an undetectable PSA (<0.1 ng/mL) at 3 months after prostatectomy. The proportion of patients achieving a PSA response will be compared between treatment arms using the Mantel-Haenszel test.

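### Secondary objective 2 concerns PSA recurrence, but its only variable is one 3-month PSA, cut at two different thresholds, which cannot tell recurrence from PSA that never cleared

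*Combined protocol and SAP*

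**What the plan says.** Section 2 (Secondary Objectives) sets objective 2 as whether treatment before surgery "diminishes the risk of PSA recurrence following prostatectomy". The plan then describes the variable for it in three places:

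- **Section 2, objectives table:** the event is a PSA of at least 0.2 "ng/ml at 3 months following prostatectomy".
- **Section 6.2.1:** "The proportion of patients with undetectable PSAs at three months will also be assessed in the two groups". No numerical limit is given there.
- **Section 8.2, PSA response rates:** "This will be defined as an undetectable PSA (<0.1 ng/mL) at 3 months after prostatectomy". The analysis is: "The proportion of patients achieving a PSA response will be compared between treatment arms using the Mantel-Haenszel test".

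More PSA is measured than these variables use. Section 6.1, footnote e, states: "Serum PSA should be obtained pre-treatment and on the day of surgery, and at 1, 2 and 3 months post operatively". It adds: "Ultrasensitive PSA testing should be run at the 1 and 2 month post-op time points". Section 3.1 applies this to all men, and footnote j requires the blood draws even when the 1- and 2-month contacts are by telephone. For the period after the 3-month visit, footnote j says only that "PSA will continue to be collected according to the treating" physician's usual routine. Section 8 plans no analysis of the 1-month, 2-month or later values.

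**The concern.** Recurrence implies that PSA first became undetectable and then returned. A single value at a fixed time, with no condition on earlier values, measures something else: whether PSA is low at month 3. Two groups of men are misplaced relative to the objective. Those whose PSA never cleared are counted with those who recurred, and those who rise after month 3 are counted with those who stay clear.

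The two cut-offs add a separate difficulty. The endpoint in the Section 2 table and the response tested in Section 8.2 are not complements of each other, so the plan does not fix one variable for this objective.

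What is at stake is what may be concluded. Read against the objective, a null 3-month comparison could be taken as no effect on recurrence, and a favourable one as a recurrence benefit. The variable supports neither.

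**Working it through.** **1. Is there a figure in the plan to reproduce?** Not for PSA. The only sample-size figure, 11 per arm in Section 8.1, is for the Gli1 endpoint (10% v 70%, two-sided alpha 0.10, power 80%). With a mean proportion of 0.4, the normal approximation gives n = [1.645·√(2·0.4·0.6) + 0.842·√(0.1·0.9 + 0.7·0.3)]² / 0.6² = 7.1. The continuity correction, (7.1/4)·[1 + √(1 + 4/(7.1·0.6))]², gives 10.2, hence 11. The figure reproduces but says nothing about PSA.

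**2. How each PSA course is scored.**

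| Course after surgery | Section 2 table (≥0.2 at 3 months) | Section 8.2 (<0.1 at 3 months) | Relative to the objective |
|---|---|---|---|
| A. Never undetectable, ≥0.2 at month 3 | event | non-responder | not a recurrence |
| B. Undetectable at 1–2 months, ≥0.2 at month 3 | event | non-responder | recurrence |
| C. 0.1 to <0.2 at month 3 | no event | non-responder | undecided |
| D. <0.1 at month 3, rises later | no event | responder | recurrence, not counted |
| E. <0.1 at month 3, stays low | no event | responder | no recurrence |

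A and B have the same entries in both scoring columns, and so do D and E. No analysis of these variables can separate the members of either pair. A and B differ only in the 1- and 2-month values, which are drawn but not analysed. D and E differ only after month 3.

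**3. Effect of the two thresholds.** Row C is where Sections 2 and 8.2 disagree. With k such men in an arm of 11, the proportion without a Section 2 event exceeds the Section 8.2 response proportion by k/11. That is 1/11 = 9.1 percentage points for one man and 2/11 = 18.2 for two.

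**4. Can a size be put on the between-arm comparison?** Section 8.2 names the Mantel-Haenszel test but gives neither a continuity correction nor a significance level for it. Take m failures among 22 men, all in the control arm. Then E = m/2, V = 11·11·m·(22 − m)/(22²·21), and χ² = (|m − E| − c)²/V, with c = 0 or 0.5.

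| Split | E | V | p, c = 0 | p, c = 0.5 |
|---|---|---|---|---|
| 3 v 0 | 1.5 | 0.679 | 1.5²/0.679 = 3.32, p = 0.069 | 1.0²/0.679 = 1.47, p = 0.225 |
| 4 v 0 | 2.0 | 0.857 | 2.0²/0.857 = 4.67, p = 0.031 | 1.5²/0.857 = 2.63, p = 0.105 |

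The smallest split that would count as significant depends on choices the plan does not state, so no single threshold is quoted here.

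**The case against.** The strongest defence is that the mismatch lies in the wording of the objective. Sections 6.2.1 and 8.2, which govern assessment and analysis, speak of undetectable PSA and PSA response and never call the variable recurrence. It is also an unpowered secondary endpoint in a 22-man phase 0 trial. Both points stand, and they are why the matter is minor. They do not remove it: Section 2 still pairs a recurrence objective with this variable, its threshold differs from Section 8.2, and the 1- and 2-month values have no planned use.

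A reader might infer several stronger things that the documents do not support:

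- **That the trial will publish a recurrence conclusion.** The analysis text does not say so. The risk is misreading.
- **That most recurrences will be missed at 3 months, by a stated fraction.** The plan gives no recurrence rate, so any fraction would come from an assumed hazard. An estimate that starts all men as cleared would also leave out the never-cleared men whom the endpoint counts.
- **That a particular split, such as 4 v 0, is needed for significance.** Under the planned test, the answer depends on the continuity correction and the level. The 0.10 level is stated only for the primary endpoint.
- **That study data collected after month 3 are being ignored.** Footnote j leaves those measurements to routine care, sets no end date, and does not say that they enter the trial data.
- **That the endpoint is really PSA persistence.** That label would repeat the fault, because row B is not persistence.

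**Conclusion.** The point holds as a mismatch between objective and variable. From the planned PSA variables the trial can describe PSA status at 3 months by arm. It cannot answer whether LDE225 lowers the risk of PSA recurrence, because never-cleared and recurrent PSA are scored alike and any rise after month 3 is not counted. Separately, Sections 2 and 8.2 define the variable with thresholds that leave 0.1 to below 0.2 ng/mL unassigned, at 9.1 percentage points per affected man in an arm of 11.

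The scoring argument rests on the plan's definitions and on the ordinary meaning of recurrence. It needs no assumed event rate. How many men would fall in each row is unknown from the documents. Severity is minor, because the primary Gli1 analysis is unaffected. The fault is in the endpoint and analysis text. Collection up to month 3 already provides what is needed for a partial separation.

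**What to change.** 1. Restate objective 2 and its endpoint neutrally, as *PSA status at 3 months after prostatectomy*, and draw no recurrence conclusion from it.
2. Reconcile the thresholds so that one definition is used in Sections 2, 6.2.1 and 8.2 and every 3-month value falls in exactly one category.
3. Add to Section 8.2 a descriptive table by arm, using the 1-, 2- and 3-month values: how many men were never undetectable, and how many were undetectable and then rising by month 3. State one cut-off that both the ultrasensitive and the standard assay can measure. The separation remains partial, since it rests on two earlier values and a single 3-month value without confirmation.

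A descriptive time-to-PSA curve beyond month 3 is optional. It would first need a statement that those values are trial data, and a cut-off date.

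The cost is a protocol amendment to Sections 2, 6.2.1 and 8.2 and one extra table. No patients, visits or assays are added for items 1 to 3. The downside is a narrower stated claim.

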### Exploratory Objectives

- (1) To evaluate genome-wide mRNA expression changes in prostate cancer induced by LDE225 exposure.

The objectives and related endpoints are summarized in the [Table](#) below.

	Objective	Endpoint	Analysis
Primary	Pharmacodynamic effect of LDE225 on prostate tissue	50% reduction in Gli1 mRNA expression comparing pre-operative prostate biopsies to radical prostatectomy specimens	qRT-PCR performed on pre-operative tumor biopsy specimens and tumor from RP specimens. Comparison performed within and between treated and untreated groups. Correlation of Gli1 levels to pre-operative Gli1 expression.
Secondary	
 
-Pathological effect on localized high-risk cancer
 
-To determine whether pre-surgical treatment with LDE225 diminishes the risk of PSA recurrence following prostatectomy
 
-To evaluate drug-related toxicities including peri-operative complications
 
	
 
-Assessment of tumor stage and grade (predicted versus actual) and changes in proliferation and apoptosis
 
-PSA <math>\geq 0.2</math> ng/ml at 3 months following prostatectomy
 
-Length of surgery, intraoperative blood loss, length of hospital stay, rates of post-operative complications (infection, wound breakdown, deep vein thrombosis, within 90 days from surgery)
 
	
 
-Routine pathologic analysis. Additionally, semi-quantitative IHC for Ki-67 and cleaved caspase-3. Comparison performed within and between treated and untreated groups.
 
-Routine serum ELISA for PSA
 
-Comparison of routinely collected intraoperative and post-operative data between treated and untreated groups
 

Exploratory	Evaluate genome-wide mRNA expression changes in prostate cancer induced by LDE225 exposure	Gene expression analysis on biopsy and prostatectomy tissue using the Affymetrix GeneChip Human Exon 1.0ST Array	Differential gene expression analysis and analysis of functional annotation comparing biopsy and prostatectomy specimens both between and within groups

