### 3      **Investigational Plan**

#### 3.1      **Overview and study design**

This pharmacodynamic/phase 0 trial is designed as a randomized two-arm (LDE225 vs. observation groups) open-label prospective clinical trial in men with localized high-risk prostate cancer undergoing radical prostatectomy.

Activation of the Hedgehog pathway is most reliably indicated by increased expression of the *GLI1* transcription factor. Quantitative RT-PCR (qRT-PCR) provides the most reliable means to assess changes in *GLI1* expression upon exposure to drug and will be used as our primary readout. Our intent will be to examine the fold change in *GLI1* expression in each man following exposure to drug (comparing pre-operative needle biopsy tissue to surgical tissue obtained from the same man's prostatectomy specimen). Because the effects of surgery and fluctuations in hedgehog signaling in the prostate are unknown, *GLI1* expression will also be compared between biopsies and prostatectomy specimens for men without drug exposure. As treatment with LDE225 may alter the gene expression of other Hedgehog pathway members and affect separate signaling pathways, as an exploratory goal, we will perform genome-wide expression analysis using the GeneChip Human Exon 1.0ST Array (Affymetrix) and will confirm fluctuations in selected genes of interest.

High-risk patients will be identified based on their core-needle biopsy features, PSA levels, and clinical stage. Eligible men (NCCN high-risk (Gleason sum  $\geq 8$ , or PSA  $>20$  or clinical stage  $\geq T3$  with no evidence of metastatic disease) will undergo a repeat prostate biopsy at Johns Hopkins with multiple (up to 12) cores taken from the area of their primary lesion. This tissue will be frozen fresh and used for analysis of *Gli1* mRNA expression and array analysis as well as mounted for pathological analysis and IHC analysis of proliferation (Ki-67) and apoptosis (cleaved caspase-3) markers.

[figure not shown]

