After obtaining baseline laboratory and clinical values (including an ECG, PSA, hematologic, and renal and hepatic panels), men will receive oral LDE225 800 mg/day or observation daily for 4 weeks ( $\pm 3$  days) prior to prostatectomy. Patients will have a clinical visit and an ECG and laboratory testing will be performed at 2 weeks and then again at 4 weeks, including a 4-week pre-prostatectomy measurement of PSA and a blood sample to determine plasma LDE225 levels by LC-MS/MS. Previous studies using other oral Hedgehog inhibitors indicate that 4 weeks will allow time for steady-state levels of drug in the plasma and for inhibition of *Gli1* expression ([LoRusso et al. 2011](#)).

Men will undergo radical prostatectomy (with bilateral pelvic lymphadenectomy as appropriate), at which point two 250-mg biopsies of prostate tissue will be obtained, frozen and stored for analysis (including *Gli1* expression, genome-wide expression analysis, intra-prostatic LDE225 levels, Ki-67, and cleaved caspase-3) with the remainder of the prostate tissue then being formalin-fixed paraffin-embedded (FFPE) and cross-sectioned for analysis as per our standard institutional procedures.

Relative fold-changes in mRNA expression of *Gli1* will be determined by first normalizing input amounts of the preoperative biopsy and prostatectomy biopsies to the housekeeping gene *HPRT1*. IHC comparisons between diagnostic biopsy specimens and prostatectomy specimens will be made by calculating immunoreactivity scores (staining intensity  $\times$  percentage cell involvement).

Protocol Version 3: October 6, 2015

All men will receive routine post-operative care, and in addition will have ultrasensitive PSA testing at 1 and 2 months post-op followed by standard PSA testing at the 3 month visit.

Study Schema

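### The plan does not provide for masking the reader of the Ki-67 and cleaved caspase-3 slides to treatment arm, although these semi-quantitative reads are compared between arms in an open-label trial.

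*Combined protocol and SAP*

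**What the plan says.** Section 3.1 describes a "randomized two-arm (LDE225 vs. observation groups) open-label prospective clinical trial", and section 3.1.2 gives the second arm no treatment before surgery.

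The first secondary objective in section 2 is whether presurgical LDE225 has a pathological effect on the tumour, with more apoptosis and less proliferation as its examples. The table in section 2 assigns this to "semi-quantitative IHC for Ki-67 and cleaved caspase-3", compared both within and between the arms. Two later sections say how the slides become numbers:

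- Section 3.1: "IHC comparisons between diagnostic biopsy specimens and prostatectomy specimens will be made by calculating immunoreactivity scores", defined as staining intensity multiplied by the percentage of cells involved.
- Section 8.2: "Ki-67 staining will be expressed as the mean staining percentage in tumor samples, reported separately for each treatment arm". Caspase-3 is summarised in the same way, with TUNEL as an additional or alternative assay.

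For both markers, section 8.2 adds: "Means will be compared across treatment arms using two-way ANOVA". Section 6.2.1 confirms that the secondary endpoints will "compare tumor stage, grade, surgical margin rates and tumor proliferation / apoptosis between treatment and observation arms".

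No section mentions coded slides, a reader masked to arm, duplicate reading or automated image analysis. Blinding appears only in a general definition in the glossary and in the SAE follow-up wording of section 7.2.2. Neither concerns the reading of slides.

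**The concern.** A semi-quantitative stain score involves judgement. Where the treatment is open and the expected direction is written into the objective, a reader who knows the arm may score treated tissue somewhat differently without intending to.

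Randomisation and the observation arm do not guard against this. They deal with baseline imbalance, and with the effects of time and surgery, which section 3.2 gives as the reason for having a control. A reading shift that follows the arm falls wholly in the between-arm contrast and looks like a drug effect. It cannot be taken out in the analysis, so the safeguard has to be in place before scoring starts.

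These two markers are the direct planned evidence on apoptosis and proliferation, in a trial that section 3.2 says should help decide whether larger studies follow.

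**Working it through.** **Inputs from the documents.** There are 11 men per arm, 22 in total (sections 3.1.4 and 8.1). The between-arm comparison is of means (section 8.2). Section 8.2 sets no significance level for the secondary endpoints. Section 8.1 uses two-sided 0.10 for the primary endpoint, and section 6.2.4 uses 0.05 for *Gli1*. Both levels are shown below.

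**The plan's own figure.** The only computed figure is the sample size for the primary endpoint, and it reproduces. With rates of 10% and 70% (mean 40%), two-sided alpha 0.10 and 80% power:

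- Uncorrected: n = (1.645·√(2·0.4·0.6) + 0.842·√(0.1·0.9 + 0.7·0.3))² / 0.6² = (1.140 + 0.461)² / 0.36 ≈ 7.1, which rounds up to 8 per arm.
- Continuity-corrected: (7.1/4)·(1 + √(1 + 4/(7.1·0.6)))² ≈ 10.2, which rounds up to 11 per arm, as stated.

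The plan gives no calculation for Ki-67 or caspase-3.

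**Assumed input.** Let d be the between-arm shift in scores, in SD units, caused by reading alone. The documents give neither an SD nor any reader-agreement figure, so d is varied over a range.

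**Method.** A two-sample t test stands in for the two-way ANOVA, because section 8.2 does not name the second factor and the ANOVA itself cannot be reproduced. With no true drug effect:

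- Degrees of freedom: 11 + 11 − 2 = 20.
- Standard error of the difference: √(2/11) = 0.426 SD.
- Noncentrality: d / 0.426 = d·√(11/2) = 2.345·d.
- False-positive rate: P(|T| > t), with T noncentral t on 20 degrees of freedom and t = 2.086 (5%) or 1.725 (10%).

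| Assumed shift d (SD) | Noncentrality | False positives, nominal 5% | False positives, nominal 10% |
|---|---|---|---|
| 0 | 0 | 5.0% | 10.0% |
| 0.1 | 0.235 | 5.6% | 10.9% |
| 0.2 | 0.469 | 7.3% | 13.5% |
| 0.3 | 0.704 | 10.3% | 17.7% |
| 0.5 | 1.173 | 20.1% | 30.7% |

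For scale, 11 per arm has 80% power to detect a true difference of about 1.26 SD at two-sided 5%. A shift of 0.3 SD is about a quarter of that (0.3/1.26 = 0.24).

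**The two scales.** Section 3.1 multiplies intensity by percentage; section 8.2 uses percentage alone. The between-arm test in 8.2 is on the percentage, which has no intensity component. The plan does not say whether both are scored or which one governs, and that leaves further choice at the reading stage.

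**The case against.** The strongest reply is that silence is not an unmasked read. The word open-label describes the treatment, not the laboratory. No reader is named, image analysis is not excluded, and slides may in practice be coded. This stands: the finding is that masking is not provided for. It still matters, because the plan as written permits an unmasked read and a later report could not point to a pre-specified safeguard.

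The false-positive rates would also follow for any unmasked read at this sample size. That stands too. They rest on assumed shifts and a substitute test, and at 0.1 SD the inflation is negligible.

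A reader might infer more than the documents support in three ways:

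- **That tumour grade and stage share the problem and the remedy.** The table in section 2 does list "Assessment of tumor stage and grade (predicted versus actual) and changes in proliferation and apoptosis", but grade and stage come from routine pathology, and section 8.2 gives no test for either. The calculation above does not apply to them, and masking them would probably need a separate research re-read.
- **That the primary endpoint is exposed.** *Gli1* is measured by qRT-PCR with software-derived threshold cycles (section 6.2.4), which leaves little room for reader judgement.
- **That the apoptosis and proliferation conclusions have no other check.** The genome-wide expression analysis could support or contradict them, although it is exploratory.

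**Conclusion.** The point holds as an omission confined to the Ki-67 and cleaved caspase-3 (or TUNEL) reads. The plan compares semi-quantitative scores between arms in an open-label trial and states no masking of the reader. Any arm-related shift in scoring would bias that comparison.

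The size of any such bias is unknown. Under the assumptions shown, the nominal 5% error rate would be about doubled by a shift of 0.3 SD and quadrupled by 0.5 SD. These figures show sensitivity; they do not predict what will happen in this trial.

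It would go too far to conclude that the reads will be unmasked, that they will be biased, or that coding would remove every source of bias. A needle core and a prostatectomy section may remain distinguishable, and drug-related change in the tissue could hint at the arm. Only secondary endpoints are affected. The change is worth making because it is cheap and cannot be made after scoring.

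**What to change.** In sections 3.1 and 8.2, state that Ki-67 and cleaved caspase-3 (or TUNEL) slides are coded by study staff before scoring. State also that the reader is masked to treatment arm, and to time point where the specimen allows, until the scores are locked.

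In the same edit, reconcile the intensity-times-percentage score in 3.1 with the mean staining percentage in 8.2, so that one scale is named for the between-arm analysis.

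The cost is a small coding workload for the specimens of 22 men. No extra reader, procedure, visit or patient is needed. Because core and prostatectomy tissue may stay recognisable, the gain is mainly for the between-arm comparison and less for the within-patient change. Routine grading and staging, and the qRT-PCR laboratory, can stay as planned.
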